6.1. Enrollment / Implant Form

An Enrollment / Implant Form is completed when a patient has completed their Enrollment visit and all required data collection is complete as outlined in Section 3.5.1.

6.2. One-Month Follow-up Form

A One-Month Follow-up Form will be completed to record all lead measurements collected during the visit.

6.3. Patient / Device Status Form

A Patient / Device Status Form will be completed when a patient or device is no longer active in the registry. Reasons for change in patient status include but are not limited to the following:

- Withdrawn
 - patient did not maintain eligibility criteria,
 - patient refused testing/follow-up
 - patient withdrawn by physician
 - patient lost to follow-up
 - out-of-service (OOS) Acuity Spiral lead (including permanent electrical abandonment)
- Patient deceased
- Patient completed five years of follow-up
- Study completed

Lead status must be reported at the time of withdrawal from the registry.

06-Dec-2012

6.3.1. Additional Information Collected at System Revision

In the event of a system revision, a detailed assessment of proximal end of lead and header at device change-outs will be required. Any newly implanted devices and system measurements will be collected similar to implant.

6.3.2. Additional Information Collected at Lead Failure

If the reason for withdrawal is lead failure, objective evidence supporting the allegation is required. Objective evidence includes but is not limited to PSA measurements demonstrating lead performance, cine recordings, x-rays; please refer to Appendix A for suggested confirmation depending on the lead failure mode. A detailed assessment of proximal end of lead and header at device change-outs will be required. Explantation data will also be requested including extraction method and tools used.

Please make every attempt to return explanted product to the manufacturer. BSC provides a Returned Products Kit (Model 6499) that can be ordered through BSC's Customer Service Department at [name] or [name] or online at www.bostonscientific.com/ppr.

6.3.3. Additional Information Collected at Patient Death

Additional data will be collected upon a patient's death:

- Was the PG explanted (Yes, No, Unknown)? Please attempt to return PG to BSC upon death.
- Was an autopsy performed (Yes, No, Unknown)?
- Was the PG interrogated "in situ" after death (Yes, No, Unknown)?
- PG status at time of death (Monitor + Therapy, Monitor Only, Off, Not Functioning, Unknown)?
- Primary organ cause (Cardiac: arrhythmic, pump function, ischemic, other cardiac, unknown; Noncardiac; Unknown).
- If ischemic (Acute, MI, Non acute MI, MI unknown).

06-Dec-2012

- Temporal course (Sudden, Nonsudden, Unknown – Presumed Sudden, Unknown).
- Antecedent worsening HF (Yes, No, Unknown).
- Operative relationship (Pre-operative, Peri-operative, Post-operative).
- Death witnessed (Yes, No, Unknown).
- Death monitored (Yes, No, Unknown).
- If death monitored (VT, Bradyarrhythmia, Pulseless electrical activity, Other, Unknown).
- If bradyarrhythmia (Sinus bradyarrhythmia, High-degree AV block with slow ventricular response, Asystole).
- Cause of death (Procedure-related, Pulse-generator-related, Lead/Catheter-related, Unknown, Other).

6.3.4. Patient Follow-up Completion

Five years of follow-up are complete when the patient has been seen on or after the five year anniversary of the ACUITY Spiral Lead implant. Centers will verify that all adverse events have been reported. Completing the Patient / Device Status Form signals the completion of the patient's participation in the LSR of ACUITY Spiral.

6.4. Patient Follow-up Log

The Patient Follow-up Log is intended to aid centers in monitoring follow-ups. This log will display the last in-clinic follow-up that has been completed as well as the timing requirements for the next in-clinic follow-up. For patients using LATITUDE, both the in-clinic and remote follow-up data are transferred directly from the device to the sponsor through the LATITUDE Patient Management system.

6.5. LATITUDE Alert Log

As described in Section 3.5.4 the LATITUDE Alert Log needs to be completed in response to LATITUDE Alerts to determine if an Adverse Event is present. Centers are

06-Dec-2012

required to investigate the Alert and determine if it should be reported as an Adverse Event.

6.6. In-Clinic Follow-up Form

In the event that data from the last in-clinic follow-up are not received via LATITUDE, an In-Clinic Follow-up Form must be completed. Electrical lead measurements from the follow-up will be collected on this form. This form can be completed retrospectively from the patient's medical record.

6.7. Adverse Event Form

The Adverse Event Form needs to be completed when reportable adverse events occur.

6.8. Deviations

Deviations are defined as any divergence from the registry protocol. Reasons for a deviation include but are not limited to: patient consent not obtained, testing incomplete/not done, and no in-clinic follow-up in over nine months.

7. PATIENT INFORMED CONSENT

Patient participation in the LSR of ACUITY Spiral is voluntary. A Patient Informed Consent form is required for all patients prior to their participation in this registry and **must be obtained** in accordance with FDA regulation 21CFR, Part 50. The Patient Informed Consent process must be followed prior to patient participation in this registry. With prior approval from BSC, the Patient Informed Consent may be modified to meet the requirements of the designated Institutional Review Board (IRB).

8. INSTITUTIONAL REVIEW BOARD

06-Dec-2012

Investigators must provide BSC with documentation of IRB approval of this registry protocol and the Patient Informed Consent form before patient enrollment in the registry begins at the center. Investigators must also provide IRB approval of revisions to the Patient Informed Consent form or amendments to the protocol.

9. CONFIDENTIALITY AND RISK ANALYSIS

9.1. Patient Data Confidentiality

All information sent to BSC (including LATITUDE data) or entered on the electronic data capture website concerning patients or their participation in the registry will be considered confidential. Authorized BSC and FDA personnel have the right to inspect and/or copy all records pertinent to the registry. Data from the registry that are used in reporting will be without identifiable reference to a specific patient.

9.2. Health Insurance Portability and Accountability Act (HIPAA)

The HIPAA requirements affect clinical trials¹ in three key areas as described below:

Accounting of Disclosures: Data collected during the conduction of prescreening activities for this registry are subject to the HIPAA accounting of disclosures' regulations. It is the responsibility of the investigative center to tell all patients whose records were screened for eligibility in the registry that their records were used in this manner if he or she requests an accounting of when his or her data were disclosed.

Consent: All patients participating in the registry will be made aware that their participation in the registry will involve disclosure of certain protected health information to BSC and for what purpose. The Patient Informed Consent form will contain a listing of the type of information that will be disclosed during the course of the clinical registry.

06-Dec-2012

Withdrawal of Consent: HIPAA specifically allows companies such as BSC that are subject to the jurisdiction of the FDA access to protected health information for activities related to the quality, safety or effectiveness of devices. This means that BSC can use data from this registry even if the individual withdraws his or her authorization.

9.3. Risks and Minimization of Those Risks

This registry does not involve any additional risks as this registry is collecting additional data consistent with approved device labeling and physician standard of care. The risks associated with this registry are those of a standard device procedure. Please see the Physician's Manual for reference.

10. MONITORING PROCEDURE

10.1. Investigator Responsibilities

The investigator is responsible for conducting the registry in accordance with the signed agreement, protocol, applicable laws, FDA regulations and any conditions of approval imposed by the reviewing IRB. An investigator may require the presence of BSC personnel at device-related procedures.

A participating Investigator shall maintain accurate, complete and current records, including record of each patient's case history and exposure to the device. Source documentation is required during acute testing, post-implant and chronic device evaluation, and adverse events. Source documentation is per Investigator's discretion but should include patient medical records, worksheets, CRFs, parameter reports, and electrograms.

NOTE: for non-BSC PGs source documentation for verification purposes will be the technical source form provided. Centers should maintain source data for all PGs (i.e programmer printouts).

06-Dec-2012

10.2. Sponsor Responsibilities

Boston Scientific will serve as the sponsor of this clinical investigation. A sponsor is defined as a person or organization that initiates, but does not actually conduct the investigation (FDA regulation 21 CFR§ 812.3 (N)). It is the responsibility of BSC as the sponsor to ensure proper monitoring of the investigation and to see that all clinical requirements are met. In addition, BSC representatives may participate in the conduct of the trial to the extent described in the following section on the role of BSC representatives. BSC personnel may or may not be blinded to the registry results. Participation in the registry will be limited to BSC personnel who are appropriately qualified and trained such as those personnel with an engineering, technical or nursing degree or equivalent training, or significant experience in cardiology, electrophysiology, or the implantable cardiovascular device industry. All personnel will be trained on the appropriate clinical study regulations and guidelines for medical device trials.

Role of Boston Scientific Representatives

BSC personnel can provide technical support to the investigator and other health care personnel (collectively HCP) as needed during implant, testing required by the protocol, and follow-ups. Support may include HCP training, addressing HCP questions, or providing clarifications to HCPs concerning the operation of BSC equipment (including programmers, analyzers, and other support equipment) or the procedures and forms related to the protocol.

At the request of the investigator and while under their supervision, BSC personnel may operate equipment during implant or follow-up, assist with the conduct of testing specified in the protocol, and interact with the patient to accomplish requested activities. Typical tasks may include:

- Interrogating the device or programming device parameters to physician requested settings

06-Dec-2012

- Performing lead diagnostic testing using a Pacing System Analyzer or programmer to obtain pacing and sensing thresholds and impedance measurements
- Clarifying device behavior, operation or diagnostic output as requested by the investigator or other health care personnel
- Assisting with the collection of study data from Pacing System Analyzers, programmers and other equipment
- Entering data on registry worksheets as long as the responsible HCP verifies and signs the completed worksheet

In addition, BSC personnel can perform certain activities to ensure registry quality. These activities may include:

- Observing testing or medical procedures to provide information relevant to protocol compliance
- Reviewing collected data and registry documentation for completeness and accuracy

Boston Scientific personnel will not:

- Practice medicine
- Provide medical diagnosis or treatment to patients
- Discuss a patient's condition or treatment with a patient without the approval and presence of the HCP
- Independently collect critical registry data (defined as primary or secondary endpoint data).
- Enter data in electronic data capture systems
- Administer and/or sign as a witness for the Informed Consent Form
- Be involved in the recruitment of patients

10.3. Registry Monitoring

A monitor and/or BSC representative may visit an investigator during the registry to assess the following criteria:

- Adherence to the protocol and applicable regulations regarding the obligations of the investigator
- Maintenance of adequate records
- Accurate registry data entry

06-Dec-2012

In the event of noncompliance (e.g. repeated failure to transfer data, multiple deviations), as determined by registry management, a monitor and/or BSC representative may attempt to secure compliance by one or more actions:

- Corresponding with the investigator
- Telephoning the investigator
- Visiting the investigator/center

If an investigator is found to be repeatedly noncompliant with the signed agreement, the protocol or any other conditions of the registry, BSC will either secure compliance or, at its sole discretion, terminate the investigator's participation in the registry.

06-Dec-2012

APPENDIX A: Glossary

Definitions based on AdvaMed's March 2009 draft *Proposal for Uniform Reporting of Clinical Performance of Cardiac Rhythm Management Pulse Generators and Leads*

Cardiac Perforation - Penetration of the lead tip through the myocardium (including microperforation) or associated venous anatomy, either clinically suspected or confirmed by chest x-ray, fluoroscopy, echocardiogram, intracardiac electrogram, and/or visually.

Conductor fracture – A mechanical break within the lead conductor (includes connectors, coils and/or electrodes) observed visually, electrically, or radiographically. Preferred confirmation is a multi-planar cine of fracture site illustrating lead fracture. X-ray displaying lead fracture also is acceptable. If explanted, return explanted lead with Suture Sleeve ligatures to lead retained.

Elevated thresholds - Sudden and significant increase in the pacing threshold value (compared to the previous measured value) at which 2:1 safety margin can no longer be achieved. Preferred confirmation is a visual confirmation that the lead has not moved (If the lead has moved see Lead migration/dislodgment). If lead revision is required, electrical lead measurements collected with PSA.

Extracardiac stimulation (e.g., phrenic, diaphragm) – Clinical observation of inadvertent muscle/nerve stimulation other than cardiac muscle.

High pacing lead impedance – Pacing impedance is considered high if a measurement is $\geq 2000^{\#}$ ohms. If a conductor fracture is suspected to be the cause the preferred confirmation is a multi-planar cine of fracture site illustrating lead fracture. X-ray displaying lead fracture also is acceptable. If explanted, return explanted lead with Suture Sleeve ligatures to lead retained.

High shock lead impedance – Shock lead impedance is considered high if a measurement is $\geq 100^{\#}$ ohms.

High shock lead impedance when attempting to deliver a shock – High shock lead impedance ($\geq 100^{\#}$ ohms) when attempting to deliver a shock.

Inappropriate shock due to oversensing – Shock delivered due to oversensing.

[#] This value is different from AdvaMed's definition to align with Boston Scientific's system guides

06-Dec-2012

Intermittent sensing - Intermittent loss of sensing or failure to detect intended intrinsic cardiac signals (atrial or ventricular) during non-refractory periods at programmed sensitivity settings

Lead insulation break or abrasion – A disruption or break in lead insulation observed visually, electrically, or radiographically.

Lead migration/dislodgment – Radiographic and electrical evidence of electrode displacement from the original implant site or electrode displacement that adversely affects pacing, and/or lead performance.

An ACUITY Spiral Lead-related adverse event will be classified as a dislodgment when the following conditions are met:

- Confirmed radiographic evidence of a lead shift
- Resulting electrical change (example: elevated thresholds, extracardiac stimulation, loss of capture)
- Requiring reprogramming or surgical intervention to correct the event

Loss of Capture - Intermittent or complete failure to stimulate cardiac depolarization at programmed settings delivered outside of the cardiac refractory period. If a conductor fracture is suspected to be the cause the preferred confirmation is a multi-planar cine of fracture site illustrating lead fracture. X-ray displaying lead fracture also is acceptable. If explanted, return explanted lead with Suture Sleeve ligatures to lead retained.

Low pacing lead impedance - Pacing impedance is considered low if a measurement is ≤ 200 ohms.

Low shock lead impedance – Shock lead impedance is considered low if a measurement is ≤ 20 ohms.

Low shock lead impedance when attempting to deliver a shock - Low shock lead impedance (≤ 20 ohms) when attempting to deliver a shock.

Oversensing / Multiple Counting – The occurrence of cardiac or non-cardiac events being misinterpreted as cardiac depolarization, (e.g., T waves, multiple counting, skeletal muscle potentials, and extracardiac electromagnetic interference).

Undersensing - Complete or intermittent loss of sensing or failure to detect the intended intrinsic cardiac signals (atrial or ventricular).

06-Dec-2012

APPENDIX B: Registry Timeline

The following is an expected schedule for conduct of the LSR of ACUITY Spiral.

Registry Initiation: BSC plans on approaching centers for participation in this registry upon FDA approval of the protocol.

Site Enrollment rate: BSC expects approximately 5 centers per month will agree to participate in the registry.

IRB approval rate: BSC expects approximately 5 centers per month will obtain IRB approval approximately within 90 days of agreement to participate.

Registry enrollment rate: Participating centers are expected to enroll 1 patient per month, with full enrollment in approximately 2 years.

Approximate enrollment completion date: Enrollment should be completed approximately 2 years following the first enrollment

Approximate last follow-up date: The last follow-up will be when the 1000th patient has his/her five year follow-up or five years post implant of the final implant, whichever occurs first.

Approximate final report submission: The final report submission will occur within 60 days following the final follow-up.

06-Dec-2012

1 PROTOCOL SUMMARY

The LSR of ACUITY Spiral Study is a prospective, non-randomized, multi-center registry of patients implanted with ACUITY Spiral Lead. The LSR of ACUITY Spiral is designed to collect product status information, any related adverse events and withdrawal data. Patient and device data from the enrollment/implant will be collected on the enrollment form. Patients will have an in-clinic full device evaluation done one month (15 to 29 days) post implant. Thereafter, it is recommended that the patient is seen for a full device evaluation at least once every six months and required at least once every 9 months. Patients may be optionally followed via the LATITUDE® remote monitoring system to facilitate ease of data collection. Upon activation in LATITUDE, data stored in the device including the latest in-clinic lead measurements will be collected via remote interrogation using the LATITUDE Patient Management system. Patients will be followed until they have completed five years of follow-up from implant or until death, withdrawal, or closure of the registry. ACUITY Spiral Leads (Models 4591, 4592, 4593) as well as other components of the implanted system are included in this registry.

2 INTRODUCTION

The primary purpose of the LSR of ACUITY Spiral is to evaluate and report on the long-term reliability and clinical performance of BSC's ACUITY Spiral Lead. Additionally system related information will be collected in this registry.

3 ENDPOINT ANALYSIS

3.1 Primary Endpoint

The ACUITY Spiral Lead will be evaluated by the chronic LV lead-related complication-free rate over a five year follow-up period. The primary endpoint analysis will include confirmed chronic LV lead related complications that result in permanent loss of therapy, invasive intervention, injury or death, and are deemed attributable to a structural lead failure by an independent Clinical Events Committee (CEC).

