4. ENDPOINTS AND DATA ANALYSIS

4.1. Endpoints

4.1.1. Primary Endpoint: Chronic LV Lead-Related Complication-Free Rate

4.1.1.1. Description and Rationale for Endpoint Selection

The ACUITY Spiral Lead will be evaluated by a chronic LV lead-related complication-free rate over a five year follow-up period.

The primary endpoint analysis will include confirmed chronic LV lead related complications that result in permanent loss of therapy, invasive intervention, injury or death.

LV lead-related adverse events within 45 days* following invasive cardiac surgery (device implant, PG change-out, cardiac catheterization, etc.) need to be reported, but will be omitted from the endpoint analysis. In addition, the following events will be collected, but will be excluded from the endpoint analysis unless determined by the Clinical Events Committee (See Section 4.2.2) to be attributed to a structural lead failure.

- Inability to place the LV lead
- Implant procedure related complications such as CS dissection, CS perforation, pneumothorax, arrhythmias, cardiac tamponade, hematoma
- LV Lead-related thrombosis
- In-patient damage to LV lead (e.g., accidental cut to lead body during pocket revision, device replacement, etc.)
- LV Lead dislodgments up to 180 days post implant procedure
- Twiddler's syndrome leading to LV lead dislodgment
- High LV pacing threshold, intermittent LV capture, no capture of LV lead
- Diaphragmatic/pectoral stimulation
- Infection
- Atrial lead, ICD lead, or generator adverse events requiring additional interventions
- Non-LV lead-related hospitalizations
- Non-LV lead-related death
- Lead revisions to optimize therapy
- Exit block
- Physiologic oversensing or undersensing

* Based on review of previous clinical studies, using a maximum of 45 days post implant gives centers an opportunity to enroll patients while allowing for a consistent time period for enrollment post implant and assessing acute adverse events without excluding adverse events that characterize long-term lead performance.

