4.2. Data Analysis

4.2.1. Endpoint Analysis

For the ACUITY Spiral Lead, the primary endpoint for this registry will evaluate the proportion of patients without a chronic ACUITY Spiral Lead-related complication within five years post-implant. When the final patient reaches five years of follow-up, the primary analysis will be based on the Kaplan-Meier method for the estimation of the five-year chronic lead-related complication-free rate, including the lower one-sided 95% confidence interval. The censoring mechanism of the Kaplan-Meier analysis incorporates all available data on patients, including those that withdraw or are lost to follow-up.

The Kaplan-Meier analysis will begin at 45 days post-implant for each patient. All patients that are successfully implanted with the ACUITY Spiral Lead and still actively followed in the study at 45 days post implant will be included in the analysis. The endpoint adverse events are defined as confirmed lead-related complications meeting the criteria in section 4.1.1.1. The

[†] The EASYTRAK lead was studied as part of the CONTAK CD/EASYTRAK Post Approval Study (PMA P010012). Mean implant duration was 26±13 months, with a cumulative implant duration of over 25,000 patient-months. The 3 year chronic lead-related complication free rate was 97.9% using Kaplan-Meier methods. Assuming a continued 1.7% annual rate (consistent with observed year to year changes in rates from previous pre-market LV lead studies) from years 3 to 5 would result in an estimated 94.5% chronic complication free-rate at 5 years for the EASYTRAK LV lead.

determination for inclusion of adverse events in the endpoint analysis will be made by an independent Clinical Events Committee. Additionally, since this registry is focused on chronic LV-lead performance, acute adverse events associated with attempted leads will not be included in this analysis as they would fall within the 45 days of an invasive cardiac surgery, therefore not meeting the criteria outlined in Section 4.1.1.1.

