3.1.2 Sample Size

Based on the calculations below, the sample size for this registry is approximately 1700 patients implanted with the ACUITY Spiral Lead with a successful LATITUDE data transmission. An exact binomial calculation with the parameters in Table 3-1: **Sample Size Parameters and Justification** was used to determine the approximate sample size necessary to detect a clinically meaningful change with 80% power and a one-sided α -level of 0.05. An annual attrition rate of 10% is assumed over the five-year follow-up.

Table 3-1: Sample Size Parameters and Justification

Primary Endpoint	N	P	Δ	95% Confidence Boundary	Justification
Chronic LV lead-related complications	1000	94.5%	2.0	92.5%	Prospectively defined based on predicate data from EASYTRAK lead*. 95% confidence boundary is clinically acceptable.

*The EASYTRAK lead was studied as part of the CONTAK CD/EASYTRAK Post Approval Study (PMA P010012). Mean implant duration was 26±13 months, with a cumulative implant duration of over 25,000 patient months. The 3 year chronic lead-related complication free rate was 97.9% using Kaplan-Meier methods. Assuming a continued 1.7% annual rate (consistent with observed year to year changes in rates from previous pre-market LV lead studies) from years 3 to 5 would result in an estimated 94.5% chronic complication free-rate at 5 years for the EASYTRAK LV lead.

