3.1.3.3 Adverse Events Included in Endpoint

The determination for inclusion of adverse events in the endpoint analysis will be made by an independent Clinical Events Committee (CEC). The adverse event will count against the endpoint if a consensus of CEC members agrees the event meets the definition

of inclusion into the endpoint. Refer to the CEC Charter (CDM00060021) for more information.

LV lead-related adverse events within 45 days following invasive cardiac surgery (device implant, PG change-out, cardiac catheterization, etc.) need to be reported, but will be omitted from the endpoint analysis. In addition, the following events will be collected, but will be excluded from the endpoint analysis unless determined by the Clinical Events Committee (See Protocol Section 4.2.2) to be attributed to a structural lead failure:

- Inability to place the LV lead
- Implant procedure related complications such as CS dissection, CS perforation, pneumothorax, arrhythmias, cardiac tamponade, hematoma
- LV Lead-related thrombosis
- In-patient damage to LV lead (e.g., accidental cut to lead body during pocket revision, device replacement, etc.)
- LV Lead dislodgments up to 180 days post implant procedure
- Twiddler's syndrome leading to LV lead dislodgment
- High LV pacing threshold, intermittent LV capture, no capture of LV lead
- Diaphragmatic/pectoral stimulation
- Infection
- Atrial lead, ICD lead, or generator adverse events requiring additional interventions
- Non-LV lead-related hospitalizations
- Non-LV lead-related death
- Lead revisions to optimize therapy
- Exit block
- Physiologic oversensing or undersensing

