5.3 FDA Requested Modified Complication-Free Rate

Per FDA feedback received on the 30-month Interim Study Status Report (P010012/R028) and subsequent amendment (A001), an additional Kaplan-Meier curve and table will be presented in each 6-month report. This analysis provides data in the form of a modified composite endpoint identical to the analyses provided for the primary endpoint with the following modifications:

- a) Chronic events occurring 30 days or greater post-implant
- b) Dislodgements occurring 30 or more days post-implant that result in permanent loss of therapy, invasive intervention, injury, or death

- c) Elevated LV pacing threshold, intermittent LV capture, and no capture of LV lead occurring 30 or more days post-implant that result in permanent loss of therapy, invasive intervention, injury, or death
- d) Diaphragmatic/muscle stimulation occurring 30 or more days post-implant that result in permanent loss of therapy, invasive intervention, injury, or death
- e) All LV lead-related perforations

Prior to each 6-month report, the study team will meet to review all new/changed adverse events since the last report to determine inclusion into the modified analysis. The study Biostatistician is responsible for keeping a spreadsheet with all adverse events and the status of inclusion into the modified endpoint.

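### SAP 3.1 requires structural lead failure for every primary-endpoint event, while Protocol 4.1.1.1 and SAP 3.1.3.3 do not, so the event set for the 92.5% test is not settled

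*SAP*

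**What the plan says.** Protocol 4.1.1.1 defines the endpoint events: "The primary endpoint analysis will include confirmed chronic LV lead related complications that result in permanent loss of therapy, invasive intervention, injury or death". It omits LV lead-related events within 45 days of invasive cardiac surgery and then gives 15 event types under the rule "In addition, the following events will be collected, but will be excluded from the endpoint analysis unless determined by the Clinical Events Committee" attributes them to structural lead failure. Protocol 4.2.1 ties the analysis to that section: "The endpoint adverse events are defined as confirmed lead-related complications meeting the criteria in section 4.1.1.1".

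SAP 3.1 restates the protocol's sentence and adds a condition on every event: "and are deemed attributable to a structural lead failure by an independent Clinical Events Committee (CEC").

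SAP 3.1.3.3 returns to the protocol's rule, with the same 15 types "excluded from the endpoint analysis unless determined by the Clinical Events Committee (See Protocol Section 4.2.2) to be attributed to a structural lead failure". One of them has a time limit: "LV Lead dislodgments up to 180 days post implant procedure". The same section lets an event count when a consensus of CEC members finds that it meets the endpoint definition, and it cites the CEC charter.

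The hypotheses (Protocol 4.1.1.2, SAP 3.1.1) set the goal at 92.5%. The sample-size sections plan on 94.5%, extrapolated from a predicate lead: "The 3 year chronic lead-related complication free rate was 97.9% using Kaplan-Meier methods". Neither document defines the predicate's event set or states a structural restriction on it.

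**The concern.** Structural failure has two different roles. In Protocol 4.1.1.1 and SAP 3.1.3.3 it is an exception that readmits a listed event. In SAP 3.1 it is a requirement for all events. The SAP thus disagrees with the protocol and with itself about which events enter its only endpoint hypothesis test.

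The SAP 3.1 rule is the stricter one, so it can only remove events and raise the complication-free rate. The goal and planning value are the same under either rule. Applied literally, SAP 3.1 would compare a smaller event count with a benchmark that carries no stated structural restriction. If the choice is left until the data are in, the results could influence which definition is used.

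**Working it through.** **1. Where the rules differ**

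| Event (serious consequence, outside the 45-day window) | Protocol 4.1.1.1 and SAP 3.1.3.3 | SAP 3.1 |
|---|---|---|
| Any structural LV lead failure | counts | counts |
| Listed type, not structural | excluded | excluded |
| Unlisted type, not structural | counts | excluded |

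Only the last row is in conflict. Examples are a dislodgment after day 180 that needs surgery and is not due to Twiddler's syndrome, or a late perforation unrelated to the implant procedure. Under SAP 3.1 taken literally, the exclusion list and its 180-day limit would have almost no function, because every non-structural event is already out.

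**2. The plan's own figures reproduce**

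- Exact binomial, N = 1000, 92.5% against 94.5%, one-sided 0.05: success at 61 or fewer events, with alpha 0.0493 and power 0.8175 (80% stated).
- Attrition: 1700 × 0.9^5 = 1004.
- Predicate: 97.9 − 2 × 1.7 = 94.5%.

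The sizing is sound. The open question is which events it applies to.

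**3. What the narrower rule could do to the test**

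Let s be the share of protocol-countable events that the CEC would call structural. The documents do not give s, so the grid below is an assumption. For a lead exactly at 92.5% under the protocol definition, the structural-only 5-year rate is 1 − 0.075 × s.

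Simulation: 1700 patients, exponential event times measured from implant, 10% annual exponential attrition, censoring at 5 years, and 20,000 trials per value. Success is S − 1.645 × SE(Greenwood) > 0.925, the bound in SAP 3.1.3.4. Monte Carlo SE is at most 0.0034.

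Expected events = 1700 × l/(l+m) × (1 − exp(−5(l+m))), with l = −ln(rate)/5 and m = −ln(0.9).

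| s | Structural-only rate | Expected events | P(success), Kaplan-Meier rule | P(success), exact binomial, N = 1000 |
|---|---|---|---|---|
| 100% | 92.50% | 99.4 | 0.06 | 0.049 |
| 98% | 92.65% | 97.5 | 0.09 | 0.070 |
| 95% | 92.875% | 94.5 | 0.15 | 0.114 |
| 90% | 93.25% | 89.5 | 0.30 | 0.227 |
| 80% | 94.00% | 79.5 | 0.72 | 0.586 |
| 75% | 94.375% | 74.5 | 0.88 | 0.767 |

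So about 5 of 99 events dropping out (s = 95%) raises the pass probability from 6% to 15%, and about 10 (s = 90%) raises it to 30%.

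**4. The same simulation at the planning value**

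If the protocol-definition rate is 94.5%, success is about 91% to 92% at s = 100%, 96% at 95% and 99% at 90%. The choice of rule matters much less there.

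**The case against.** The strongest reply is that SAP 3.1 is an introductory summary and SAP 3.1.3.3 the operative section. The latter is devoted to which adverse events count, repeats the protocol's list and exception, and gives the CEC counting rule. Letting the specific section govern yields the protocol's rule and keeps the 180-day limit meaningful. This is a sensible reading, and under it nothing changes. But no text gives that order of precedence, and SAP 3.1 states an inclusion condition in plain terms. The CEC is told to apply the endpoint definition, and the SAP holds two. The charter may settle practice, but it is not among the documents and would not reconcile them.

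Other points have partial force:

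- **Narrow event set.** The list already removes threshold and capture problems, stimulation, infection and more. Nothing shows that s is as low as 75% to 80%, so those rows are illustrative only.
- **Undefined predicate.** If the predicate count was structural-only, SAP 3.1 would match the goal better than the protocol does. The pass probabilities at 92.5% are false-pass rates only if the protocol definition is the right one. This is a reason to settle the definition and the goal together.
- **Visibility to FDA.** SAP 5.2 commits to six-monthly tables showing whether each adverse event was adjudicated as counting. SAP 5.3 adds a modified analysis that includes "Dislodgements occurring 30 or more days post-implant that result in permanent loss of therapy, invasive intervention, injury, or death" and all LV lead-related perforations. Events would not vanish unseen. However, the SAP 5.3 analysis uses a different window and event set, the study team decides inclusion, and no 92.5% test is stated.
- **Deliberate refinement.** SAP 5.5 allows analysis changes through a SAP, but the added condition is not flagged as a change and SAP 3.1.3.3 keeps the protocol's rule.

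**Conclusion.** The concern holds, and the inconsistency must be fixed before the 5-year analysis. The SAP gives two incompatible rules for which events are tested against 92.5%, and one of them departs from the protocol. The direction is certain: SAP 3.1 can only remove events and favour the device.

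The size is unknown. It is zero if SAP 3.1.3.3 governs or if every protocol-countable event is structural. The illustrative increase, from 6% to 15% or 30% with 5% or 10% of events removed, rests on an assumed s, a lead exactly at the protocol null, exponential event and attrition times, and the protocol definition being the one to which 92.5% belongs. No claim is made that inflation has occurred.

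**What to change.** Through a revised SAP approved before the 5-year analysis, as SAP 5.5 provides, delete the structural-failure clause from SAP 3.1 and keep the statement that the CEC decides inclusion. SAP 3.1 then agrees with Protocol 4.1.1.1 and SAP 3.1.3.3. Confirm that the CEC charter uses the same definition and that events already adjudicated were judged by it. A structural-only rate can be reported as supportive, without the 92.5% test.

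The cost is one clause and two checks. The reported rate may also be less favourable than under SAP 3.1. At the protocol null the difference is 7.5 × (1 − s) percentage points: about 0.4 (0.375) at s = 95% and 0.75 at s = 90%.

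If a structural-only primary endpoint was intended, amend Protocol 4.1.1.1 and SAP 3.1.3.3 instead, and re-justify 92.5% and 94.5% on predicate data with the same event definition. That route costs a protocol amendment and a new justification of the goal.
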